4.4.3.1 Gastrointestinal Disorders

Gastrointestinal perforation, GI fistula, and intra-abdominal and pelvic abscess:

Prior to initiation of treatment with cabozantinib, subjects should be carefully evaluated for potential risk factors including (but not limited to) the following:

- Tumors invading GI or respiratory tracts.
- Active peptic ulcer disease, inflammatory bowel disease (e.g., ulcerative colitis, Crohn's disease), diverticulitis, cholecystitis or symptomatic cholangitis, or appendicitis.
- History of abdominal fistula, GI perforation, bowel obstruction, or intra-abdominal abscess.
- Ongoing visceral complications from prior radiation therapy.
- Prior GI surgery (particularly when associated with delayed or incomplete healing).

Complete healing following abdominal surgery and radiation therapy and/or resolution of intra abdominal abscess must be confirmed prior to initiating treatment with cabozantinib.

After starting cabozantinib, subjects should be monitored for early signs of GI perforation such as abdominal pain, nausea, emesis, constipation, and fever especially if known risk factors for developing GI perforation or fistula (Turnage et al. 2008) are present.⁴³

Discontinue cabozantinib and initiate appropriate management in subjects who have been diagnosed with GI perforation or fistula.

Diarrhea: Subjects should be instructed to notify their physician immediately at the first signs of poorly formed or loose stool or an increased frequency of bowel movements. Guidelines for the evaluation and management of diarrhea are shown Table 0-3 below.

Administration of antidiarrheal/antimotility agents is recommended at the first sign of diarrhea as initial management. Some subjects may require concomitant treatment with more than one antidiarrheal agent. When therapy with antidiarrheal agents does not control the diarrhea to tolerable levels, cabozantinib should be temporarily interrupted or dose reduced. When the diarrhea is controlled, retreatment with cabozantinib may be acceptable per Investigator decision.

In addition, general supportive measures should be implemented such as continuous oral isotonic hydration, correction of fluid and electrolyte abnormalities, small frequent meals, and stopping lactose-containing products, high-fat meals, and alcohol.

Recurrent or prolonged diarrhea can be associated with anal or perianal skin erosions which increase the risk for anal abscesses, fistulas, or proctitis. Good personal hygiene should be emphasized. Regular examinations of the perianal region should be performed whenever diarrhea has occurred during treatment with cabozantinib. Infections of the perianal region should be treated per local guidelines.

Table 0-3: Management of Diarrhea Associated with Cabozantinib

Event	Management
Tolerable Grade 1-2 (duration < 48 h)	
 Continue with study treatment and consider dose reduction. Initiate treatment with an antidiarrheal agent (e.g., loperamide 4 mg followed by 2 mg after each episode of diarrhea [maximum: 16 mg loperamide per day]). Dietary modifications (e.g., small lactose-free meals, bananas and rice). Intake of isotonic fluids (1-1.5 L/day). Re-assess after 24 hours: 
 Diarrhea resolving to baseline bowel habits: gradually add solid foods and discontinue or decrease antidiarrheal treatment after 12 h diarrhea-free interval. Diarrhea not resolving: Continue/resume antidiarrheal treatment .
Intolerable Grade 2, Grade 2 > 48 h, or ≥ Grade 3	
 Interrupt study treatment. Ask subject to attend clinic. Rule out infection (e.g., stool sample for culture). 
 Administer antibiotics as needed (e.g., if fever or Grade 3-4 neutropenia persists > 24 h). Administer fluids (1-1.5 L/day orally or IV, as appropriate) for hydration or to correct electrolyte abnormalities. For Grade 3-4 or complicated lower grade diarrhea consider hospitalization and IV hydration. Re-assess after 24 h. 
 Diarrhea resolving to baseline bowel habits or Grade ≤ 1: consider restarting study treatment at reduced dose. Diarrhea not resolving: Start and or continue antidiarrheal treatment (e.g., loperamide 4 mg followed by 2 mg after each episode of diarrhea [maximum: 16 mg loperamide per day]). Consider starting second line antidiarrheal or referral to gastroenterologist.

4.4.3.2 Nausea and Vomiting

Antiemetic agents are recommended as clinically appropriate for treatment or prophylaxis of nausea and vomiting, along with supportive care. Dehydration and electrolyte abnormalities may be associated with vomiting and monitoring for and correction of fluid and electrolyte disturbances should be implemented.

Antiemetic medications should be assessed for potential drug interactions (refer to [Section 4.5.3](#) for further details).

4.4.3.3 Non-Gastrointestinal Fistula

Radiation therapy (in certain areas of the body) has been identified as a possible predisposing risk factor for fistula formation in subjects undergoing treatment with cabozantinib.

Subjects with any clinically relevant ongoing complications from prior radiation therapy (e.g., radiation esophagitis or other inflammation of the viscera) should not be treated with cabozantinib until these complications have resolved.

Radiation therapy to the thoracic cavity (including mediastinum) should be avoided within 4 weeks of starting treatment with cabozantinib (excluding local radiation for bone metastases). Fistula should be ruled out as appropriate in cases of onset of severe mucositis or difficulty swallowing after start of therapy. Discontinue cabozantinib and initiate appropriate management in subjects who have been diagnosed with a non GI fistula.

4.4.3.4 Hemorrhage

Hemorrhagic events, including serious and sometimes fatal events, have been reported with cabozantinib. Subjects should be evaluated for potential bleeding risk factors prior to initiating cabozantinib treatment and should be monitored for bleeding events with serial complete blood counts and physical examination while on study. Risk factors for hemorrhagic events may include (but may not be limited to) the following:

- Tumor of the lung with cavitary lesions or tumor lesions which invade or encase major blood vessels. NSCLC with squamous cell differentiation is known for significant lung cavitations and centrally located tumors that may invade major blood vessels. Thus, the anatomic location and characteristics of

tumor as well as the medical history should be carefully reviewed in the selection of subjects for treatment with cabozantinib.

- Recent or concurrent radiation to the thoracic cavity.
- Active peptic ulcer disease, inflammatory GI diseases including Crohn's disease and ulcerative colitis.
- Underlying medical conditions which affect normal hemostasis (eg, deficiencies in clotting factors and/or platelet function, or thrombocytopenia).
- Concomitant medication with anticoagulants or other drugs which affect normal hemostasis.
- History of clinically significant hemoptysis, hematemesis, or hematuria.

The risk of hemorrhage in cabozantinib-treated subjects with brain metastases has not been thoroughly analyzed. Though the incidence of CNS hemorrhage events in a study of subjects with glioblastoma was higher than observed in general population of subjects with cancer treated with cabozantinib, it is not clear how the risk of hemorrhage in glioblastoma translates to a risk of hemorrhage for subjects with brain metastases. Currently, brain metastases of carcinomas are not contraindications to the use of cabozantinib, but subjects with brain metastases should be monitored with a high index of suspicion if symptoms that could be due to a CNS hemorrhage occur.

Complete healing from radiation-induced side effects should have occurred before initiating cabozantinib treatment, and cabozantinib should be discontinued in subjects with serious and life-threatening bleeding events or recent hemoptysis (≥ 2.5 mL of red blood).

4.4.3.5 Thromboembolic Events

Thromboembolic events are frequent in cancer subjects due to procoagulant changes induced by the malignancy or anticancer therapy. DVT and pulmonary embolism have been observed in clinical studies with cabozantinib, including fatal events. Subjects

who develop a pulmonary embolism and/or DVT should have study treatment interrupted until therapeutic anticoagulation is established. Treatment with cabozantinib may be resumed in subjects with pulmonary embolism or DVT if it is determined that the event is uncomplicated and that the subject is deriving clinical benefit from cabozantinib treatment and that anticoagulation does not place them at a significant risk that outweighs the benefit of resuming treatment per discretion of the investigator and according to individual protocols. Low molecular weight heparins are the preferred management for thrombotic events; oral anticoagulants (e.g., warfarin or other coumarin-related agents, direct thrombin or direct FXa inhibitors, or antiplatelet agents, or chronic use of aspirin above low dose levels for cardioprotection per local applicable guidelines) are not allowed.

Arterial thrombotic events (e.g., TIA, MI) have been observed in studies with cabozantinib. Further treatment with cabozantinib should be discontinued in subjects who develop an acute MI, cerebral infarction, or any other clinically significant arterial thromboembolic complication.

4.4.3.6 Hypertension

Table 0-4 provides treatment guidelines for hypertension deemed related to cabozantinib.

Blood pressure should be monitored in a constant position visit to visit, either sitting or supine in a relaxed setting.

Decisions to reduce or interrupt the dose of study treatment must be based on BP readings taken by a medical professional and must be confirmed with a second measurement at least 5 minutes following the first measurement.

Cabozantinib should be discontinued in subjects with hypertensive emergency.

Table 0-4: Management of Hypertension Associated with Cabozantinib

Event	Management
Subjects NOT receiving optimized anti-hypertensive therapy	

> 140 mm Hg (systolic)^a and < 160 mm Hg
 
OR
 
> 90 mm Hg (diastolic) and < 110 mm Hg
	
 Optimize antihypertensive medications by adding new or additional antihypertensive medications and/or increase dose of existing medications. Reduce cabozantinib treatment by one dose level if optimal antihypertensive therapy (usually to include 3 agents) does not result in BP <140 mm Hg systolic or <90 mm Hg diastolic If subject is symptomatic interrupt cabozantinib treatment

≥ 160 mm Hg (systolic)
 
OR
 
≥ 110 mm Hg (diastolic)
	
 Reduce cabozantinib by one dose level^b or interrupt cabozantinib treatment per Investigator discretion. Add new or additional anti-hypertensive medications and/or increase dose of existing medications and monitor subject closely for hypotension. If optimized antihypertensive therapy (usually to include 3 agents) does not result in BP < 140 mm Hg systolic or < 90 mm Hg diastolic, cabozantinib treatment should be dose reduced further or interrupted. Cabozantinib treatment should be dose interrupted if upper limits of systolic BP (≥ 160 mm Hg) are sustained and not adequately manageable or if systolic BP is > 180 mm Hg or diastolic BP > 110 mm Hg, or if subject is symptomatic. Re-start cabozantinib treatment at the most tolerable dose and re-escalate only if BP falls to and is sustained at < 140 mm Hg systolic and < 90 mm Hg diastolic.
Hypertensive emergency ^c	
 Discontinue cabozantinib treatment.

^a Permitted dose levels are defined by individual protocols.
 
^b Hypertensive emergency is defined as uncontrolled elevated BP with clinical evidence of progressive or impending end-organ damage (e.g., myocardial infarction/ischemia, intracranial hemorrhage, cerebral ischemia, pulmonary edema, encephalopathy, kidney damage).
	

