Grade 3 or 4	Interrupt temozolomide and cabozantinib until $\geq 100 \times 10^9/L$. Dose reduce temozolomide by 1 dose level. Continue cabozantinib at the same dose or reduce dose by one level-at the investigator's discretion. At platelet count of $< 10 \times 10^9/L$ discontinue temozolomide.

Hypertension	
> 140 mm Hg (systolic) ^a and < 160 mm Hg OR > 90 mm Hg (diastolic) and < 110 mm Hg	
 Optimize antihypertensive therapy. Reduce cabozantinib treatment by one dose level if optimal antihypertensive therapy (usually to include 3 agents) does not result in BP <140 mm Hg systolic or <90 mm Hg diastolic. Continue temozolomide at the current dose
≥ 160 mm Hg (systolic) OR ≥ 110 mm Hg (diastolic)	
 Reduce cabozantinib by one dose level or interrupt cabozantinib treatment per investigator discretion. Re-start cabozantinib treatment at the most tolerable dose and re-escalate only if BP falls to and is sustained at < 140 mm Hg systolic and < 90 mm Hg diastolic. 
Interrupt/continue temozolomide at the investigator's discretion.

Hypertensive emergency ^a	
 Discontinue cabozantinib treatment
^a Hypertensive emergency is defined as uncontrolled elevated BP with clinical evidence of progressive or impending end-organ damage (e.g. myocardial infarction/ischemia, intracranial hemorrhage, cerebral ischemia, pulmonary edema, encephalopathy, kidney damage).	
Hand-foot Syndrome (PPES)	
Grade 1	
 Cabozantinib treatment may be continued at the current dose if PPES is clinically insignificant and tolerable. Otherwise, cabozantinib should be reduced to the next lower dose level. ^a Start urea 20% cream twice daily AND clobetasol 0.05% cream once daily. 
Reassess at least weekly; if PPES worsens at any time or does not improve after 2 weeks, proceed to the intervention guidelines for Grade 2.
 
 Continue temozolomide at the current dose.

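### Table 0-4 directs a cabozantinib interruption on five blood-pressure triggers; Appendix A, covering the same rows, leaves four to discretion and does not mention the fifth, and no text says which governs

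*Combined protocol and SAP*

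**What the plan says.** Section 4.4.3.6, Table 0-4, has an upper row entered at "≥ 160 mm Hg (systolic") or "≥ 110 mm Hg (diastolic"). Its first bullet allows a one-level reduction "or interrupt cabozantinib treatment per Investigator discretion". A later bullet in that row reads "Cabozantinib treatment should be dose interrupted if upper limits of systolic BP (≥ 160 mm Hg) are sustained and not adequately manageable" and continues "or if systolic BP is > 180 mm Hg or diastolic BP > 110 mm Hg, or if subject is symptomatic". The lower row (systolic above 140 and below 160, or diastolic above 90 and below 110) calls for optimised antihypertensives, then a one-level reduction if they fail, and separately tells the site to interrupt cabozantinib if the subject is symptomatic.

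The Hypertension block of Appendix A uses the same two rows. Its upper row says "Reduce cabozantinib by one dose level or interrupt cabozantinib treatment per investigator discretion", followed by the restart and re-escalation sentence and a discretionary line on temozolomide. Its lower row keeps the optimisation and reduction steps and continues temozolomide.

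Both places discontinue cabozantinib for hypertensive emergency.

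**The concern.** A site that opens Appendix A sees a complete-looking hypertension algorithm with the same row limits as Table 0-4 but without its directed interruptions. Nothing on that page suggests that more instructions exist elsewhere. Two sites following the protocol in good faith could treat the same reading differently.

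The main stake is subject safety. Section 4.4.3 lists hypertension among the events seen in at least 20% of cabozantinib-treated subjects and among those with early onset, so the situation can arise within the 12 weeks of the primary endpoint. A secondary stake is that the dose received in that period could depend on which page a site uses, in a multicentre single-arm trial with no control group against which to judge it.

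**Working it through.** No sample size, power or error rate is involved, so the check is a side-by-side comparison of the cabozantinib action for each trigger. Subjects in hypertensive emergency are set aside because the two texts agree there.

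| Situation | Table 0-4 | Appendix A | Same action? |
|---|---|---|---|
| Systolic above 180 | Interrupt | Reduce one level or interrupt, at discretion | No |
| Diastolic above 110 | Interrupt | Reduce one level or interrupt, at discretion | No |
| Systolic 160 or more, sustained and unmanageable | Interrupt | Reduce one level or interrupt, at discretion | No |
| Upper row with symptoms | Interrupt | Reduce one level or interrupt, at discretion | No |
| Lower row with symptoms | Interrupt | Optimise antihypertensives; reduce one level if that fails; symptoms not mentioned | No |
| Systolic 160 to 180, diastolic 110 or less, no symptoms, not sustained | Reduce one level or interrupt, at discretion | Same | Yes |
| Hypertensive emergency | Discontinue | Discontinue | Yes |

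Count of differing triggers: 4 in the upper row + 1 in the lower row = 5.

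Two examples show what this means in use.

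- A subject at 190/115, short of an emergency, is to be held under Table 0-4. Under Appendix A the investigator may hold or may continue one level down.
- A symptomatic subject in the lower row is to be held under Table 0-4. Under Appendix A read alone, cabozantinib continues at the current dose while antihypertensives are optimised.

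The next question is whether other text settles the difference.

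- Section 4.4 refers the reader to Appendix A for dose-modification algorithms, and Section 4.4.4 repeats the reference.
- Of the two tables, only Appendix A gives a temozolomide instruction for hypertension, so sites have a reason to use it.
- Within Appendix A, the diarrhea block points back to Table 0-3 and the proteinuria block to Table 0-6. The hypertension block has no pointer to Table 0-4.
- Section 4.4.3.6 requires a second measurement before a dose decision. That confirms the reading; it does not select the action.
- No sentence ranks Table 0-4 and Appendix A.

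**The case against.** The best defence is that a careful site would reach Table 0-4 anyway. Section 4.4 presents Appendix A as something to take into account, and it allows cabozantinib to be interrupted at any time at the investigator's discretion. The footnote to Table 0-2 directs readers to Section 4.4.3, where Table 0-4 sits. Table 0-2 itself calls for interruption at Grade 3 unless a dose reduction and optimal care manage the event easily. Interrupting also complies with every line in both tables. All of this is correct and lowers the chance of harm. It does not remove the difference: permission to interrupt is not a direction to interrupt, and the Table 0-2 footnote does not help a reader who has gone straight to Appendix A.

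A reader might infer four stronger points. The documents do not support them.

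- **Appendix A leaves out interruption altogether.** It does not. Its upper row keeps interruption as an option; what is absent is the directed interruption.
- **Table 0-4 contradicts itself.** The discretionary bullet followed by the conditional one reads naturally as a general rule limited by a specific one.
- **Diastolic discretion has no width, because the row opens at 110 and interruption starts above 110.** The row is also entered on systolic pressure, so discretion remains for an asymptomatic subject with systolic 160 to 180 and diastolic up to 110, provided the elevation is not sustained and unmanageable. A narrow diastolic margin contradicts nothing.
- **The blood-pressure goal is inconsistent.** The reduction step applies if therapy "does not result in BP <140 mm Hg systolic or <90 mm Hg diastolic", while the restart step says to "re-escalate only if BP falls to and is sustained at < 140 mm Hg systolic and < 90 mm Hg diastolic". These govern two different decisions, and the second may be stricter by intent. Appendix A uses the same two wordings, so this is not a difference between the tables.

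**Conclusion.** The point holds as an inconsistency between two parts of the protocol. On five triggers, Table 0-4 directs a cabozantinib interruption that Appendix A leaves to discretion (four, upper row) or does not mention (one, lower row). Continued dosing in the upper row means dosing one level down.

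The conclusion rests on two assumptions: that sites may use Appendix A on its own, which the references in Sections 4.4 and 4.4.4 make plausible, and that the wording in Table 0-4 is meant to direct and not merely to advise.

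The documents give no frequency for readings above 180 or 110, or for symptomatic hypertension, so the number of subjects affected and the effect on dose over 12 weeks cannot be estimated. The 20% figure in Section 4.4.3 concerns hypertension in general and should not be read as the frequency of these triggers. Any effect on the primary endpoint is indirect. The reason to act is safety and uniform conduct across sites.

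**What to change.** The sponsor's medical team should reconcile the hypertension instructions in Table 0-4 and Appendix A so that both give the same cabozantinib action for each of the five triggers. Alternatively, the protocol should state which of the two governs and add a cross-reference in the Appendix A hypertension block, as the diarrhea and proteinuria blocks already have. Which action applies at which reading is for that team, and no view is taken here.

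The cost is amendment wording in two tables and notice to the sites. Nothing changes in the sample size, the assessments or the analysis.

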4.4.3.7 Stomatitis and Mucositis

Preventive measures may include a comprehensive oral examination to identify and treat any potential risk for complications before study treatment is initiated. Appropriate correction of local factors should be instituted as indicated, such as modification of ill-fitting dentures and appropriate care of gingivitis. During treatment with cabozantinib, good oral hygiene and standard local treatments such as non-traumatic and non-irritating cleansing, and oral rinses (e.g., with a weak solution of salt and baking soda) should be maintained. Lips should be kept moisturized with lip balm. The use of lipstick, lip-gloss, and Vaseline should be avoided.

Local treatment should be instituted at the earliest onset of symptoms. Obtain bacterial/viral culture if oral infection is suspected and treat infection as clinically indicated.

4.4.3.8 Skin and Subcutaneous Tissue Disorders

Wound healing and surgery: Cabozantinib has the potential to cause wound healing complications and wound dehiscence which may even occur long after a wound has been considered healed. Therefore, surgical and traumatic wounds must not only be completely healed prior to starting cabozantinib treatment but must also be monitored for wound dehiscence, wound infection and other signs of impaired wound healing while the subject is being treated with cabozantinib. If dehiscence occurs, cabozantinib treatment should not be restarted until complete healing has taken place.

Treatment with cabozantinib should be stopped at least 3 weeks prior to elective surgery. Do not administer cabozantinib for at least 2 weeks after major surgery and until complete wound healing.

4.4.3.9 Palmar-plantar Erythrodysesthesia Syndrome

PPES; also known as hand-foot syndrome, skin rash (including blister, erythematous rash, macular rash, skin exfoliation, dermatitis acneiform, and pappular rash), pruritus, dry skin, erythema, pigmentary changes, and alopecia have been reported with cabozantinib. All subjects on study should be advised on prophylactic measures including the use of emollients, removal of calluses, avoidance of exposure of hands and feet to hot water leading to vasodilatation, protection of pressure-sensitive areas of hands and feet, and use of cotton gloves and socks to prevent injury and keep the palms and soles dry. Early manifestations include tingling, numbness, mild hyperkeratosis, and symmetrical red and swollen areas on the palms and soles. The lateral sides of the fingers or periungual zones may also be affected. Adequate interventions are required to prevent worsening of skin symptoms such as blisters, desquamations, ulcerations, or necrosis of affected areas. Analgesics may be required for pain control. Aggressive management of symptoms is recommended, including early dermatology referral. Treatment recommendations in response to PPES are summarized in Table 0-5.

Table 0-5: Management of Hand-Foot Syndrome (PPES) Associated with Cabozantinib

CTCAE v.5.0 Grade	Action To Be Taken
Grade 1	
 • Cabozantinib treatment may be continued at the current dose if PPES is clinically insignificant and tolerable. • Otherwise, cabozantinib should be reduced to the next lower dose level. • ^a Start urea 20% cream twice daily AND clobetasol 0.05% cream once daily. • Reassess at least weekly; if PPES worsens at any time or does not improve after 2 weeks, proceed to the intervention guidelines for Grade 2.
Grade 2	
 • Cabozantinib treatment may be continued if PPES is tolerated. • Cabozantinib should be dose reduced or interrupted if PPES is intolerable. • Continue urea 20% cream twice daily AND high potency steroid cream (e.g., clobetasol 0.05%) once daily and add analgesics (e.g., NSAIDs/gamma-aminobutyric acid agonists) for pain control if needed. • Reassess at least weekly; if PPES worsens or affects self-care, proceed to the intervention guidelines for Grade 3.
Grade 3	
 • Interrupt cabozantinib treatment until severity decreases to Grade 1 or 0. • Continue treatment of skin reaction with high potency steroid cream (e.g., clobetasol 0.05%) twice daily AND analgesics. • Resume study drug at a reduced dose if PPES recovers to Grade ≤ 1. • Discontinue subject from study treatment if PPES does not improve within 6 weeks.
CTCAE, Common Terminology Criteria for Adverse Events; NSAID, non-steroidal anti-inflammatory drug; PPES, palmar plantar erythrodysesthesia syndrome. ^a Permitted dose levels are defined by individual protocols.	

